1 PROTOCOL SUMMARY

1.1 SYNOPSIS

| | |
|---------------------------|---|
| Title: | Bariatric Embolization of ArTeries with imaging visibLe EmbolicS (BEATLES) |
| Study Description: | The BEATLES study is an investigator-initiated, prospective, double-blinded, randomized, sham-controlled study that will assess the impact of bariatric embolization on the systemic levels of obesity-related hormones and, as a consequence, on weight loss. The goal of this study is to help treat obesity combining a lifestyle program and a minimally invasive, angiographic (i.e., through blood vessels) approach. |
| Objectives: | 
Primary Objective: To determine the efficacy of the BAE procedure using radiopaque 100-200 µm microspheres (BTG-001933) for weight loss in obese patients.
 
Secondary Objectives: To determine the safety and further explore the efficacy of the BAE procedure using radiopaque 100-200 µm microspheres (BTG-001933) for weight loss in obese patients
 |
| Endpoints: | 
Primary Endpoint: Change in body weight 12 months after randomization
 
Primary Safety Endpoints: All adverse events until the end of the study (12 months)
 |

| | |
|---|---|
| | Secondary Endpoints: |
| | 1) All adverse events until day 30 post embolization |
| | 2) Change in body weight at timepoints other than 12 months |
| | 3) Percentage change in body weight |
| | 4) Achievement of >5% reduction in body weight |
| | 5) Percentage excess weight loss (EWL) |
| | 6) Change in multi-compartment body fat composition as measured by MRI |
| Study Population: | 59 adult men and women, ages 21-70 years, with a body mass index (BMI) $\geq 35 \text{ kg/m}^2$ and otherwise suitable for protocol therapy at the Johns Hopkins Hospital |
| Phase: | 2 |
| Description of Sites/Facilities | 1 site: Johns Hopkins Hospital |
| Enrolling Participants: | |
| Description of Study Intervention: | Minimally invasive, non-surgical, angiographic bariatric embolization (BAE) of the left gastric and/or gastroepiploic arteries using investigational 100-200 μm radiopaque microspheres (BTG-001933, Biocompatibles UK, Ltd) |
| Study Duration: | 3 years |
| Participant Duration: | 12 months |

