4 STUDY DESIGN

4.1 OVERALL DESIGN

We hypothesize that transvascular bariatric embolization of the left gastric and/or gastroepiploic arteries will result in safe and effective weight loss in obese participants compared to control subjects.

The BEATLES study is an investigator-initiated, prospective, phase 2, single-site, double-blinded, randomized, sham-controlled study that will assess the impact of bariatric embolization on the systemic hormonal levels of obesity and weight loss in 54 obese participants (BMI ≥ 35 kg/m 2) at post-procedure weeks 1 and 2, and months 1, 3, 6, and 12. There will be 10 pilot patients (See Statistical Analysis below for sample size calculations) for a total of 59 participants. Participants will be followed with study outcomes assessed for a period of 12 months. The duration of the study will be approximately three years.

The goal of this study is to help treat obesity using a minimally invasive, angiographic (i.e., through blood vessels) approach. This study will be conducted under an FDA Investigational Device Exemption (IDE) to support the use of 100 – 200 μ m BTG-001933 microspheres in bariatric artery embolization for the treatment of obesity. The BTG-001933 microsphere (Biocompatibles UK, LTD) is an investigational device based on the legally marketed LC Bead LUMITM (K152157, K162373), which has an approved indication for use of embolization of hypervascular tumors and arteriovenous malformations. The BTG-001933 microsphere is the result of modification of the LC Bead LUMITM with respect to bead size range and iodine content. These device modifications may facilitate and optimize imaging techniques associated with the planned procedure.

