5.5 STRATEGIES FOR RECRUITMENT AND RETENTION

The targeted patient cohort is men and women aged between 21 and 70 years of various racial and ethnic backgrounds. Vulnerable patients (pregnant women, those who lack consent capacity, prisoners, children, employees, etc.) will be excluded as per the inclusion and exclusion criteria.

It is anticipated that approximately 1300 patients will be pre-screened to enroll 59 eligible subjects (based on prior experience in the BEAT Obesity trial) over a 24-month period. All subjects will be enrolled at the Johns Hopkins Hospital. Pre-screening will utilize an existing registry of patients from previous trials and patient referrals (weight management clinic referrals and self-referrals from advertising campaign). Identified or referred patients will be screened by phone using a telephone script.

Subjects will be followed for a period of 12 months. Retention strategies will include collecting multiple methods for contacting each participant and visit reminders. Subjects will receive payments of up to \$945 after the bariatric embolization (or control) procedure per the 12-month period, using the payment scheme tabulated below. Payment is given at 5 different intervals. Each test or log must be completed within the allotted range in order to receive payment. Payment may be prorated for weight management visits. For example, if a participant attended 4 weight management visits instead of 5 during weeks 4-8, they may receive \$40 during that time.

| Weeks 1-3 | Weeks 4-8 | Months 3-5 | Months 6-11 | Month 12 |
|------------------------------------|------------------------------------|------------------------------------|------------------------------------|----------------------------------|
| Food Log \$30 | Food Log \$20 | Food Log \$20 | Food Log \$30 | Food Log \$40 |
| Hunger Satiety \$30 | Hunger Satiety \$20 | Hunger Satiety \$20 | Hunger Satiety \$30 | Hunger Satiety \$50 |
| Hormone Test \$20 | Hormone Test \$30 | Hormone Test \$35 | Hormone Test \$40 | Hormone Test \$50 |
| | | MRI \$45 | MRI \$50 | MRI \$50 |
| | | Endoscopy \$70 | | |
| Weight Mgmt. (3 visits) \$40 | Weight Mgmt. (5 visits) \$50 | Weight Mgmt. (6 visits) \$55 | Weight Mgmt. (7 visits) \$60 | Weight Mgmt. (1 visit) \$5 |
| Blood Tests \$10 | Blood Tests \$10 | Blood Tests \$10 | Blood Tests \$10 | Blood Tests \$15 |
| Total \$130 | Total \$130 | Total \$255 | Total \$220 | Total \$210 |

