6.3 MEASURES TO MINIMIZE BIAS: SITE TRAINING RANDOMIZATION AND BLINDING

Of the 59 participants who will participate in this research, 27 participants will be randomized to the intervention arm, and 27 participants will be randomized to the control arm. The first 10 patients to meet all eligibility criteria will be the 10 pilot patients; these patients will not be analyzed with the randomized patients.

In this double-blind experiment, neither blinded study team nor participants will know the details of the participants' randomization. Unblinded members of the study team will perform the procedure and have access to the medical record in case of emergency. All study visits involving study intervention and the details of the procedure, including start/stop times, will be recorded on the relevant eCRF by the unblinded team member.

All participants will undergo the same preparation for the procedure, then, when the procedure begins, the participants will be blindfolded with a head drape and will have their hearing damped with ear plugs and noise-cancelling headphones, preventing them from seeing and hearing the procedure, but still allowing them to keep in contact with the procedure team. All procedure images and reports, regardless of the randomization arm, will be kept with the unblinded member of the study team, and will not be housed centrally. All participants will adhere to the same follow-up schedule, meeting with blinded members of the study team only. The procedural team will not have further contact with the participant, the participant will only be followed by the blinded study team.

After all subjects complete the follow-up period, the study team and the subjects will each complete a survey to determine to which arm they thought each subject was randomized. After the surveys are completed, both the investigator and subject will be unblinded at the same time. Once the study is closed all reports and images will be entered into the clinical record.

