9.2 SAMPLE SIZE DETERMINATION

Sample sizes per randomized treatment arm for the proposed study are based on providing sufficient power for testing the primary hypothesis that BAE leads to larger mean weight loss from baseline than a sham procedure.

Based on previous data, it is anticipated that the mean weight loss from baseline at 12-months post-randomization in the BAE arm will be at least 8 kg.(21, 36, 37) In contrast, we expect that participants in the sham arm will lose 3.3 kg at 12 months (corresponding to 3% weight loss from a baseline weight of 110 kg). Also, a common standard deviation for the change in weight from baseline at 12 months of 7 kg is assumed based on the data from the prior BEAT Obesity trial. Using a two-sample t-test and a two-sided alpha of 0.2, 21 participants in each arm will provide 80% power. The sample size is increased to 27 participants in each arm (i.e. a total of 54 randomized participants) to take account of an expected 20% drop-out rate by the time of the 12-month assessment. Since this is a phase 2 study, it is appropriate to use a two-sided alpha greater than the standard 0.05 value.

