9.3 POPULATIONS FOR ANALYSES

Statistical analyses will follow the intent-to-treat paradigm, meaning all participants will be analyzed according to the treatment group to which they were randomized. However, we will also perform an analysis according to a modified intention-to-treat (mITT) paradigm. As defined here, mITT means that all participants will be analyzed based on the treatment arm to which they were randomized, provided that they had exposure to the treatment protocol in their assigned arm. Participants who are randomized to a particular treatment arm, but who do not receive exposure to this treatment will be considered as 'mis-randomized', and will not be included in the mITT population. Reasons for participant mis-randomization include: 1) discovering post-randomization that a given participant does not meet the inclusion / exclusion criteria and is subsequently withdrawn from the study, 2) a participant refuses treatment after randomization, 3) a clinical investigator refuses to treat a participant post-randomization according to the protocol for the treatment arm to which the participant was assigned for any reason, and 4) the participant withdraws from the study post-randomization, but prior to receiving exposure to study treatment, for any reason.

The ten pilot participants recruited in the proposed trial will not be analyzed with the participants recruited through randomization. Rather, these ten pilot participants will be used to test and refine the trial protocol, and data collection procedures.

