9.4.6 PLANNED INTERIM ANALYSES

An interim analysis of safety and technical utility of the embolic device (image visibility) and procedural assessments such as blinding, will be done after the 10 pilot patients complete the embolization procedure. Study reports on device/ procedure related complications are to be sent to the FDA following treatment of the ten (10) pilot patients and then after every 10 additional subjects are randomized and treated (blinded).

No interim analysis for efficacy or futility are planned.

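### The enrolment figures do not add up (54 randomized + 10 pilots = 64, not 59), and protocol and SAP put the interim safety analysis and first FDA report after 10 and 5 patients respectively

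*Protocol*

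**What the plan says.** **Total.** The protocol gives 59 in five places. The synopsis describes the population as "59 adult men and women, ages 21-70 years". Section 4.1 has "There will be 10 pilot patients (See Statistical Analysis below for sample size calculations) for a total of 59 participants". Section 5.5 plans that "approximately 1300 patients will be pre-screened to enroll 59 eligible subjects". Section 6.3 opens with "Of the 59 participants who will participate in this research, 27 participants will be randomized to the intervention arm, and 27 participants" to control. Section 10.1.6 schedules a DSMB meeting once all 59 have been treated.

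**Randomized.** Section 4.1 gives 54, section 6.3 gives 27 per arm, and section 9.2 derives "a total of 54 randomized participants". SAP 3.8 repeats the same derivation.

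**Pilots.** Section 6.3 says "The first 10 patients to meet all eligibility criteria will be the 10 pilot patients", and section 9.3 says "The ten pilot participants recruited in the proposed trial will not be analyzed with the participants recruited through randomization".

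**Interim analysis and FDA reports.** Protocol 9.4.6 says the interim look at safety, image visibility and procedural matters "will be done after the 10 pilot patients complete the embolization procedure". The first FDA report on complications is tied to the same 10 patients, and section 10.1.6 repeats 10 for the report to the DSMB and FDA. SAP 5.8 describes the same analysis and the same report in nearly identical terms, but after 5 run-in patients. Both documents then call for a report after each further 10 randomized and treated patients.

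**Precedence.** SAP 1.0 says the SAP overrides the protocol's analytical plans where they differ.

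**The concern.** The total, the number of non-randomized embolizations and the report trigger are figures that staff act on, and as written they cannot all be followed. There are two linked problems.

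1. Within the protocol, 54 randomized, 10 pilots and 59 in total are mutually incompatible.
2. Between the documents, the same safety analysis and the same first FDA report fall after 10 patients or after 5. Because of the precedence clause in SAP 1.0, a reader cannot simply default to the protocol for the interim analysis.

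At stake are the enrolment ceiling under the IDE, how many people are exposed to an investigational device, how many of them are embolized before the first formal look, and when the DSMB believes treatment is complete. The primary test, its alpha and the analysis populations are not at stake.

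**Working it through.** **Inputs**

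| Quantity | Value | Source |
|---|---|---|
| Mean loss, BAE / sham | 8 kg / 3.3 kg | Protocol 9.2, SAP 3.8 |
| SD of weight change | 7 kg | same |
| Alpha, target power | 0.20 two-sided, 80% | same |
| Drop-out | 20% | same |
| Randomized | 27 + 27 = 54 | Protocol 4.1, 6.3, 9.2; SAP 3.8 |
| Pilots | 10 | Protocol 4.1, 6.3, 9.3, 9.4.6, 10.1.6 |
| Run-in patients | 5 | SAP 5.8 |
| Total | 59 | Protocol 1.1, 4.1, 5.5, 6.3, 10.1.6 |

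**Step 1. Is the 54 sound?** The difference is 8 − 3.3 = 4.7 kg. For a two-sample t-test with n per arm, the noncentrality parameter is 4.7 / (7 × √(2/n)) on 2n − 2 degrees of freedom. At n = 20 exact power is 0.794; at n = 21 it is 0.809. So 21 per arm is the smallest number reaching 80%. Inflating for drop-out, 21 / (1 − 0.20) = 26.25, rounded up to 27 per arm, or 54. The plan's figure reproduces.

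**Step 2. Does the total follow?**

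- 54 + 10 = 64, which is 5 more than 59.
- 54 + 5 = 59, which matches but contradicts every statement of 10 pilots.
- 59 − 10 = 49 randomized, which contradicts 27 + 27.

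The 10 pilots cannot sit inside the 54: section 6.3 takes them as the first eligible patients and keeps them out of the randomized analysis, and section 9.3 contrasts them with those recruited through randomization.

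**Step 3. What each resolution implies**

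| Resolution | Total | Randomized | Receive the device |
|---|---|---|---|
| 54 + 10 | 64 | 54 | 27 + 10 = 37 |
| 54 + 5 | 59 | 54 | 27 + 5 = 32 |
| 49 + 10 | 59 | 49 | 24 or 25 + 10 = 34–35 |

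Under 54 + 10, a DSMB meeting taken literally at 59 treated falls at randomized patient 59 − 10 = 49, with 54 − 49 = 5 still untreated.

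**Step 4. Power, only under 49 + 10.** Evaluable patients: 49 × 0.8 = 39.2, or 19.6 per arm. Exact power is 0.778 at 19 per arm, 0.788 at 19.6 (a fractional size, used for interpolation) and 0.794 at 20. This compares with 0.809 at the planned 21 and, on the same basis, 0.817 at 54 × 0.8 / 2 = 21.6 per arm.

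**Step 5. Report timing.** First report and interim analysis: after 10 treated (protocol) or 5 (SAP). Later reports, counted as all patients treated: 20, 30, 40… or 15, 25, 35…. Counted as randomized patients only, they fall at 10, 20, 30… under either document, so what really moves is the first report and the interim analysis, by 5 embolized patients.

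**The case against.** The number on which the primary inference rests, 54 randomized, is the same wherever it is stated, and the pilots are outside the randomized analysis. Neither document plans an interim efficacy or futility look, so the estimand, alpha and test are untouched. The 49 + 10 resolution has no support in the text, and it is the only one that costs power. The figures look like an incomplete change from 5 to 10 pilots. Safety oversight does not hang on this trigger alone: section 10.1.6 has the DSMB meet after the first 5 non-randomized participants and at least semi-annually, section 7.1 halts the study for evaluation on a single listed event, and section 8.3.5 requires serious events to be reported within 24 hours.

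Most of this is fair, and it limits the consequences. The power loss is small and should carry little weight. The DSMB meeting after 5 is compatible with 10 pilots and is not part of the conflict. SAP precedence covers analytical plans, so it bears on the interim analysis more clearly than on FDA reporting, which section 10.1.6 also sets as a matter of oversight. The DSMB meeting at 59 was presumably meant to fall when treatment is complete.

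None of it removes the contradiction. The explanation of an incomplete update is an inference: the amendment history table in section 10.4 is blank, and nothing in the text reviewed says which count is intended.

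**Conclusion.** The concern holds. The stated total and its parts differ by 5 participants (64 against 59), and protocol and SAP differ by 5 embolized patients on when the interim safety analysis and first FDA report occur. It must be fixed, because the enrolment ceiling, the number of non-randomized embolizations, a DSMB milestone and a regulatory report trigger all depend on it.

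It does not threaten the primary analysis if 54 are randomized. If 49 were, power would be about 79%, assuming the plan's 4.7 kg difference, 7 kg SD, alpha of 0.20 and 20% drop-out. The conclusion on the counts needs no assumption beyond the protocol's own separation of pilots from randomized patients. The study schema and title page were not available for review and may show the intended count.

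**What to change.** Choose one set of numbers and make every section agree:

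- **54 + 10 = 64.** Correct the total in the synopsis and in Protocol 4.1, 5.5, 6.3 and 10.1.6, and the 5 in SAP 5.8. The pre-screening estimate in 5.5 also needs review: at the same yield, 1300 × 64 / 59 is about 1,410.
- **54 + 5 = 59.** Correct each statement of 10 pilots in Protocol 4.1, 6.3, 9.3, 9.4.6 and 10.1.6. SAP 5.8 then already agrees.
- **49 + 10 = 59.** Restate the randomized number in Protocol 4.1, 6.3 and 9.2 and in SAP 3.8, give power as about 79%, and align SAP 5.8.

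Under any choice, state one trigger for the interim analysis and first FDA report, identically in Protocol 9.4.6, Protocol 10.1.6 and SAP 5.8. Tie the final-treatment DSMB meeting to the corrected total. The meeting after the first 5 non-randomized participants need not change. Use one name for these patients, since the protocol uses run-in for the weight-management period.

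The cost is text in two documents, with no change of method. The protocol text needs an amendment with the IRB and FDA approvals described in its Statement of Compliance; raising enrolment to 64 is the more substantive request.

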4.2 SCIENTIFIC RATIONALE FOR STUDY DESIGN

Due to the psychological basis for weight loss, a sham control procedure is required for comparison. All patients will receive weight management support, which is routine care for this patient population.

4.3 JUSTIFICATION FOR DOSE

The standard embolization technique utilized for the study was chosen based on animal studies to create ischemia. Ischemia is a reduction in blood flow, which is the mechanism that causes the cells in target area (fundal region of stomach) to down regulate ghrelin hormone production without necrosis. During the embolization process beads will be infused (under CT imaging) until stasis of anterograde arterial flow is achieved. It is believed that lower ghrelin levels result or correlate with suppressed appetite or lowered hunger response.

4.4 END OF STUDY DEFINITION

A participant is considered to have completed the study if he or she has completed all phases of the study including the last visit or the last scheduled procedure shown in the Schedule of Activities (SoA), Section 1.3.

The end of the study is defined as completion of the last visit or procedure shown in the SoA in the trial globally.

5 STUDY POPULATION

5.1 INCLUSION CRITERIA

In order to be eligible to participate in this study, an individual must meet all of the following criteria:

1. Male or female, aged ≥ 21 and ≤ 70 years
2. Willing, able, and mentally competent to provide written informed consent
3. Obese patients with a BMI $\geq 35 \text{ kg/m}^2$
4. Weight $\leq 400 \text{ lb}$
5. Vascular anatomy (including celiac, hepatic, and gastric arteries) that in the opinion of the interventional radiologist is amenable to bariatric embolization, as assessed via 3D CT angiography
6. Suitable for protocol therapy, as determined by the interventional radiology investigator
7. Adequate hematologic (neutrophils $> 1.5 \times 10^9/\text{L}$, platelets $> 70 \times 10^9/\text{L}$, INR < 1.5), hepatic (bilirubin $\leq 2.0 \text{ mg/dL}$, albumin $\geq 2.5 \text{ g/L}$), and renal (estimated GFR $> 60 \text{ mL/min. } 1.73 \text{ m}^2$) function
8. For females of reproductive potential: agreement to use of highly effective contraception for duration of study participation
9. Patients who have failed conservative weight loss therapies such as supervised low-calorie diets combined with behavior therapy and exercise
10. Live or work within 65 miles of the enrolling institution in case a catastrophic post-embolization event occurs

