8.2.5 Blood, Urine, and Stool Tests

Blood tests including complete blood count, tests of liver and kidney function, serum albumin measurement, electrolytes, urea, creatinine measurements (EUC), and fasting chemistries, including glucose and insulin, will be performed at screening (and again before the procedure if the screening blood tests were done more than 30 days before the procedure) and every study visit thereafter (week 1, week 2, week 4, month 3, month 6, month 12).

A stool occult blood test to identify gastrointestinal bleeding and H. pylori blood antibody test to see if the participant has been exposed to a specific type of bacteria that can cause stomach ulcers will be performed only at screening.

All clinical laboratory assays will be performed at the Johns Hopkins CORE laboratory according to the laboratory's normal procedures. Reference ranges will be supplied by the laboratory and used to assess the laboratory data for clinical significance and out of range pathological changes. Abnormal laboratory values which are unexpected or not explained by the patient's clinical condition should be repeated until confirmed, explained or resolved. Changes from screening will be recorded as an adverse event if clinically significant.

The following clinical laboratory assessments will be completed at specified study visits during the study.

Biochemistry

- Sodium
- Potassium
- Calcium
- Blood Urea Nitrogen
- Creatinine
- Albumin
- Total Protein
- Aspartate transaminase (AST)
- Alanine transaminase (ALT)
- Alkaline phosphatase (ALP)
- Total and indirect bilirubin
- Glucose
- Lactate Dehydrogenase (LDH)
- Insulin
- Pancreatic enzymes: Amylase and Lipase

Coagulation

- Prothrombin Time (PT)
- Partial Thromboplastin Time (PTT)
- International Normalized Ratio (INR)

Hematology

- Hemoglobin
- Hematocrit
- White Blood Cell (WBC) Count
- Platelet Count
- WBC Differential and ANC
- Red Blood Cell (RBC) Count
- Mean corpuscular volume (MCV)

Lipid Profile

- Low-Density Lipoprotein (LDL)
- High-Density Lipoprotein (HDL)
- Triglycerides
- Total Cholesterol
- Total Cholesterol: HDL Ratio
- Non-HDL Cholesterol

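### The albumin limit in inclusion criterion 7 is written as 2.5 g/L (0.25 g/dL), so the albumin element of the hepatic-function criterion excludes no one at plausible albumin values

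*Protocol*

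**What the plan says.** Protocol section 5.1 makes every inclusion criterion binding: "In order to be eligible to participate in this study, an individual must meet all of the following criteria". Criterion 7 asks for adequate hematologic, hepatic and renal function. Its hepatic part has two numeric limits, "bilirubin $\leq 2.0 \text{ mg/dL" and "albumin $\geq 2.5 \text{ g/L".

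This is the only numeric albumin limit in either document. Protocol section 8.2.5 lists albumin among the screening bloods ("tests of liver and kidney function, serum albumin measurement, electrolytes, urea, creatinine measurements (EUC") but attaches no unit or cut-off to it, and on normal values says only: "Reference ranges will be supplied by the laboratory". The SAP does not mention albumin.

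The limit is meant to be applied. Section 8.1 compares initial laboratory results with repeat results from within 30 days of the procedure to confirm eligibility. Section 8.2.15 has clinical laboratory data reviewed against the criteria and the decision recorded on an eCRF.

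**The concern.** A lower limit on albumin is there to stop candidates whose albumin is too low. A limit of 2.5 g/L is a small fraction of any albumin value one would expect to see in a screened candidate, so the element looks inert.

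Two things are at stake. First, one of the two measures that criterion 7 names for hepatic function does no screening ahead of an investigational arterial embolization. Second, the written reference for eligibility is unsound. Staff who follow the text apply an empty test. Staff who apply some other unit depart from the approved text, and section 10.1.10 counts any noncompliance with the protocol as a deviation. The electronic data system has automatic range checks (section 10.1.9.1). A check built on the written limit would not fire at plausible values, and one built on another unit would disagree with the protocol.

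**Working it through.** **Inputs from the documents**
- Albumin limit: at least 2.5 g/L (Protocol 5.1, criterion 7).
- Bilirubin limit in the same criterion: at most 2.0 mg/dL.
- Albumin reference range: none given (Protocol 8.2.5 leaves it to the laboratory).

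**Input assumed**
- Serum albumin in candidates of 20 to 50 g/L, from markedly low to normal.

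**Step 1: convert the limit as written.** There are 10 dL in 1 L, so g/dL = (g/L) / 10, and 2.5 / 10 = 0.25 g/dL. The protocol derives this limit from nothing else, so there is no stated calculation to reproduce.

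**Step 2: compare the limit with the assumed range.** Multiple of the limit = albumin / 2.5.

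| Assumed albumin (g/L) | Multiple of the written limit | Excluded as written? |
|---|---|---|
| 20 | 20 / 2.5 = 8 | No |
| 25 | 25 / 2.5 = 10 | No |
| 30 | 30 / 2.5 = 12 | No |
| 35 | 35 / 2.5 = 14 | No |
| 50 | 50 / 2.5 = 20 | No |

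No value in the range fails. At the bottom of the range, albumin would have to fall by a further factor of 8 to reach the limit.

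**Step 3: size of a possible unit slip.** If the same number were read in g/dL, it would be 2.5 × 10 = 25 g/L, ten times the written limit. This shows how much turns on the unit. It does not establish what was intended.

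**Step 4: look for a correction elsewhere.** Section 8.2.5 gives no albumin unit or cut-off, sections 8.1 and 8.2.15 refer back to the eligibility criteria, and the SAP is silent. Nothing overrides criterion 7.

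**Step 5: check the reach into the statistics.** The sample size (Protocol 9.2, SAP 3.8) uses mean losses of 8 and 3.3 kg, an SD of 7 kg, alpha 0.2 and 20% drop-out. The primary comparison (Protocol 9.4.2, SAP 5.3) uses weight change. Neither uses albumin.

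**The case against.** **Other safeguards remain.** A reader might infer that the trial has no working hepatic or bleeding screen. The documents do not support that. Criterion 7 keeps its bilirubin and INR limits. Section 5.2 excludes cirrhosis, known portal venous hypertension, prior hepatic surgery, prior liver embolization and ASA class 4 or 5. Criterion 6 and exclusion 34 leave room for investigator judgement, and section 8.1 has two physicians screen each participant. Nothing in the documents identifies a candidate who would pass all of this and be stopped only by a corrected albumin limit. This objection stands, and it confines the point to the albumin element.

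**Mixed units prove little.** It is tempting to argue that albumin must be wrong because bilirubin beside it is per decilitre. But criterion 7 also states neutrophils and platelets per litre, so mixed denominators are normal there. The point rests on the size of the limit, not on this contrast.

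**The unit may have been lost in reading the PDF.** The GFR unit in the same criterion is malformed in the text as read, so a dropped letter cannot be ruled out. Against that, the bilirubin unit in the same criterion is intact. An artefact is possible but not shown, and the source file would settle it.

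**Inconsistent reading across sites.** A reader might expect this, but there is one site, and the clinical assays run in one core laboratory. What remains is narrower: the site's working rule may differ from the written one. The eligibility eCRF is not among the documents, so it may already carry a different unit.

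**Staff will know what was meant.** Perhaps, but that would be an undocumented reading of a binding limit. The statement of compliance requires documented FDA and IRB approval for changes to the protocol.

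**Conclusion.** The point holds in a limited form. As written, the albumin limit is 0.25 g/dL, and the albumin element of criterion 7 excludes no one whose serum albumin lies between 20 and 50 g/L. That range is an assumption, because the documents give none. The conclusion is the same across all of it, with values 8 to 20 times the limit.

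That the unit was meant to be g/dL is a plausible explanation, not something the documents show; the number, the unit or both may need correcting. There is no effect on power or on the primary test. In principle an unclear criterion could touch the analysis sets, since Protocol 9.3 drops from the mITT population participants found ineligible after randomization and withdrawn, but nothing in the documents suggests this would involve more than a few people. This is an operative eligibility limit that should be corrected, at modest priority.

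**What to change.** - Check the protocol source file to see whether the unit there matches the text.
- Have the sponsor's clinical team confirm both the intended albumin limit and its unit. No value is proposed here.
- Correct criterion 7 so that it agrees with the core laboratory's reporting unit, and make sure the eligibility eCRF and any automatic range check use the same limit and unit.

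The cost is a short text correction and, if needed, a change to one range check. It needs the usual FDA and IRB approval, so it is best carried with another amendment. No change to the sample size or the planned analyses follows from it.
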